Attention bias modification methods have been studied in other fields, such as anxiety and substance use disorders. Attention retraining (AR), a method to reduce an unwanted AB, is effective at reducing AB to problem cues in other fields, such as anxiety and substance use in adults (85-87) and pediatric anxiety (88). AR has been shown to effectively reduce AB and intake of chocolate, a palatable food (89, 90), or to increase biases for and intake of healthy foods (91). Among adults, five retraining sessions had a lasting effect of reducing AB to food for at least a week after training was concluded (92). Additionally, there is preliminary evidence among adults with LOC eating that AR is effective in reducing attention bias and LOC eating episodes immediately and 3-months following delivery (93). There are no data in adolescents. One preliminary study of 20 overweight and obese children found that a single session of AR in the laboratory reduced AB and food intake (94). Yet, there are no data among youth with reported LOC eating – a subgroup that appears to have a particularly robust AB to palatable foods (54).

Given the initially promising results from single sessions of AR to reduce AB youth (94), it is plausible that AR in the natural environment may have a potent effect. Learning theory posits that the development of new behaviors is strongly context dependent (95). The ubiquity of palatable unhealthy foods makes it necessary to provide an AR intervention that will generalize outside of the laboratory in order to impact AB and, ultimately, body weight.

[figure not shown]

Fig 2. Attention retraining in the natural environment reduces biases to highly palatable foods that, in turn, decreases LOC eating and consumption of highly palatable foods.

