second session, participants will be asked to return for a brief visit to perform the anatomical MRI scan. Contingent on the availability of the scanner, the participants may be scheduled to complete the anatomical MRI on a day separate from their study visit. They will be compensated for their time. A urine sample will be obtained from all participants and tested for pregnancy on the day of the participant's anatomical MRI scan. If a participant has undergone an anatomical MRI scan at the NIH of sufficient quality in the preceding two months, she will not be required to complete another MRI anatomical scan as part of this study.

7. **Smartphone training.** Participants will be given the mobile devices with attention retraining or the control program. Before they leave the laboratory, they will be trained in the use of the mobile devices and provided with contact information of the study staff to aid with troubleshooting of any problems that might arise. The training will take approximately 20 minutes.

Attention Retraining or Control Program with Ecological Momentary Assessment (EMA) in the Natural Environment for 2 Weeks. Participants will be randomized in blocks of 8 with stratification for LOC status (LOC vs. no-LOC), race/ethnicity (Hispanic/Non-Hispanic, Black/White), and age (12-14; >14) to attention retraining or control programs carefully matched for intensity of interaction. In addition to three attention retraining or control trials administered on the smartphone each day, attention bias will be assessed once a day. Each of the four daily trials will also include an EMA component in which participants answer questions regarding their eating patterns and mood in real time. A sample administration schedule for a school day is presented in Figure 3.

Figure 3. Sample administration schedule.

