On school days, youth will be signaled to complete AR/control trainings and EMA assessments pre-school (Training 1) and immediately post-school (Training 2). They will also be signaled 2 more times (at random) between 3:30 pm (or end of school day) and bedtime, once for training (Training 3) and once for AB assessment (in random order). Bedtime will be set individually with each participant based on the participant's and participant's parent's preference. Adolescents tend to go to sleep between 10:45PM and 11PM on school nights (153), therefore the latest bedtime offered will be 10:30PM. Bedtimes will be offered in 30-minute increments and the earliest bedtime available will be 7:30PM. In sum, on each study day participants will be scheduled to complete 3 AR/Control trainings (80 trials each) and one AB assessment (40 trials). On non-school days, the same schedule will be used except that the first training may be delayed by up to 2 h. A different picture set will be used on each day (order randomized over time), and assessments will occur using pictures on which youth were scheduled to receive training. With

>70% compliance, participants will complete ~30 AR/Control trainings during the two weeks, and AB will be assessed ~10 times during the study.

- 1. Attention retraining / control program on smartphone.** For the attention retraining task, the probe always replaces the neutral picture. There is a perfect correlation between picture type and probe location. Over time, individuals assigned to the attention retraining group should learn to attend away from the highly palatable pictures. For the control, the probe is equally likely to replace the food picture and the neutral picture. There is no correlation between picture type and probe location, and no training of attention should occur. This control has been used in previous attention retraining studies (154, 155). It ensures that: 1) the duration of attention retraining and control trials should not differ; 2) attention retraining and control participants receive equal practice on the motoric aspects of the visual probe tasks; and 3) attention retraining and control participants are exposed to the same food and neutral stimuli.

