Data from the MEG acquisition computer will be transferred to the analysis computer and then copied to DVD and external hard drive. DVD's will be labeled with the assigned participant ID, date, and session type (i.e., social threat or food cue). Each participant's data will be stored on the secure RAID serve for several weeks and then permanently deleted. All participant data files will be labeled with the participant's ID. Electronic data will be password protected and accessible only by authorized study personnel. Electronic (de-identified) data will be backed up daily and stored at a secure server. All hardcopy data will be locked in [name] storage cabinets in research offices at the NIH CRC and will be accessible only by authorized study personnel. All data will be collected specifically for the purpose of the current proposed research project.

Data will be stored for a minimum of 3 years after completion of analyses for this study. Furthermore, in compliance with federal law, records will be maintained until all subjects enrolled in the study have reached a minimum age of 23 years. Subjects may choose to withdraw from the study at any time and may request for stored data to be destroyed. All withdrawals from the study will be documented and included in the annual report for continuing review by the IRB.

b. Publication of Research Findings

We estimate that several publications will result from this study; for example, comparison of

changes in neural responding and attention bias in LOC and No-LOC girls assigned to the AR vs. control condition, as well as the impact of these potential changes on eating behaviors and body composition over time. The impact of the booster intervention will also be evaluated. Findings will be submitted to peer-reviewed journals, and data will be deposited as required by governmental rules.

c. Primary Outcomes

Specific Aim 1: Examine change in attention bias following a 2-week attention retraining or control period.

- i. **Primary outcomes:** Change in laboratory measured attention bias (i.e., reaction times to palatable foods at the baseline laboratory visit vs. the post-EMA visit),
- ii. **Secondary outcomes:** Change in EMA-measured attention bias over time (2-week period), laboratory measured AB to social threat (i.e., reaction times to threatening stimuli at the baseline laboratory visit vs. the post-EMA visit),

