1. Post-smartphone program lab visit and the 3-month follow-up visit reaction time data from dot probe task will be using a general linear model (or appropriate generalized linear model depending upon distribution diagnostics) controlling for baseline visit reaction time data from dot probe task, and covariates (order effects, age, race, and BMIZ).
2. Reaction time data from EMA

Specific Aim 2

- a. **Hypothesis 2:** General linear model adjusting for baseline neural activity and covariates (order effects, age, race, and BMIZ), will be used to analyze

1. Post-smartphone visit and 3-month follow-up visit neural activity in response to palatable food cues in the “bottom-up” attention circuitry (ventral ACC, OFC, insula, and striatum) in the unconscious reaction period.
2. Post-smartphone visit and 3-month follow-up visit neural activity in response to palatable food cues in the “top-down” attention circuitry (dorsal ACC, vLPFC, dlPFC) in the attention deployment period.

Specific Aim 3

- a. **Hypothesis 3A:** Youth randomized to AR and control groups will be compared on
 1. Post-smartphone program lab energy intake from laboratory test meal using a general linear model (or appropriate generalized linear model depending upon distribution diagnostics) controlling for the baseline visit energy intake and covariates
 2. The daily number of LOC episodes using a generalized estimating equations (GEE) model with a negative binomial response function controlling for baseline LOC episodes and covariates. The model will include a main effect for group, and a group-by-time interaction. Analyses use all available data (no imputation). We will also examine LOC as a continuous daily dependent variable (mean of 3 LOC items).
 3. BMI and adiposity at the 3-month follow-up visit using a general linear model (or appropriate generalized linear model depending upon distribution diagnostics) controlling for baseline lab visit and the post-smartphone program lab visit BMI and adiposity.

Exploratory Aim 1

- a. Youth randomized to AR (who receive the AR program at 3 months as a booster) will be compared to controls (who receive AR for the first time) at post-booster visit and the 6-month follow-up visit on BMI, adiposity, and energy intake using a general linear model (or appropriate generalized linear model depending upon distribution diagnostics) controlling for Visit #2 measurement

Exploratory Aim 2

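### Smartphone attention bias has no untrained starting value, so a within-program change or slope would miss the early part of any retraining effect; the between-arm contrast should be specified instead

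*Combined protocol and SAP*

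**What the plan says.** All references are to the combined protocol and SAP.

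- **Daily order (Section VI.b, Attention Retraining or Control Program with EMA).** On school days, "youth will be signaled to complete AR/control trainings and EMA assessments pre-school (Training 1) and immediately post-school (Training 2"). Two further signals follow later in the day, "once for training (Training 3) and once for AB assessment (in random order"). On other days "the same schedule will be used except that the first training may be delayed by up to 2 h". Each day holds "3 AR/Control trainings (80 trials each) and one AB assessment (40 trials").
- **Start of the phone program (Section VI.b, Visit #2, item 7).** Only instruction in using the device is listed: "The training will take approximately 20 minutes". No phone AB assessment is listed at that visit, and the document does not say whether signals begin that afternoon or the next day.
- **Outcome (Section VII.c, Specific Aim 1).** The smartphone measure is secondary: "Change in EMA-measured attention bias over time (2-week period"). The primary outcome is laboratory AB, which is measured at Visit 2 before any training.
- **Analysis (Section VII, Determination of Sample Size and Analytic Plan, Hypothesis 1).** The stem says that the randomized arms are to be compared. The smartphone entry beneath it is, in full, "Reaction time data from EMA". The laboratory entry above it names a model, a baseline term and covariates.
- **Expected speed of effect (Section III, Attention Retraining).** A preliminary study of 20 children is cited in which "a single session of AR in the laboratory reduced AB and food intake".

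**The concern.** A change outcome needs a starting value that treatment has not touched. Here the first scheduled phone value in the AR arm already carries whatever the first trainings have done, while the control arm has had no active training. If the arms are then compared on first-to-last change, or on the slope across days, the early part of the effect cancels out of the contrast. If the effect builds steadily in one direction, the error is always toward no effect.

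The protocol's own rationale makes some early effect plausible, since it cites a reduction after one session. Hypothesis 1B, the natural-environment half of Hypothesis 1, rests on this measure.

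There is a second risk. An analyst who copies the laboratory model, which adjusts for a baseline, may take the first phone value as that baseline. It is a post-randomization value affected by treatment, so adjusting for it would remove part of the effect being tested.

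**Working it through.** **1. Reproduce the plan's own counts.** With 14 days, 3 trainings and 1 AB assessment a day, and 70% compliance:
- trainings: 14 x 3 x 0.70 = 29.4, against the plan's figure of about 30;
- AB assessments: 14 x 1 x 0.70 = 9.8, against about 10;
- all prompts: 14 x 4 = 56, matching the number in the compensation section.

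The schedule is therefore read as the plan intends.

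**2. Position of the first AB assessment.** Trainings 1 and 2 come first; Training 3 and the AB assessment follow in random order. With every prompt answered on a full first day, the assessment follows 2 trainings (probability 0.5) or 3 (0.5). That is 2 x 80 = 160 or 3 x 80 = 240 trials, with a mean of 200. If the phone goes live on the afternoon of Visit 2, so that Training 1 is skipped, it follows 1 or 2 trainings. Non-school days keep the order.

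**3. Missed prompts.** Assume each prompt is answered independently with probability 0.70. The chance that a girl's first completed AB assessment follows no completed training is, on day 1, 0.5 x (0.3² x 0.7) + 0.5 x (0.3³ x 0.7) = 0.041. Later days add almost nothing. With an afternoon start it is 0.5 x (0.3 x 0.7) + 0.5 x (0.3² x 0.7) = 0.137. So about 4% (or 14%) would supply an untrained value, and only through non-compliance. Simulation under the same assumption gives a mean of 2.6 completed trainings before the first completed assessment on a full first day.

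**4. Share of the effect missed by a first-to-last change.** The last assessment, on day 14, follows 13 x 3 + 2 = 41 or 13 x 3 + 3 = 42 trainings, so 41.5 on average. Let k be the trainings before the first assessment. The learning curves are assumptions; none is in the documents.
- Linear accrual: share = k / 41.5.
- Exponential accrual with a half-life of h trainings: share = (1 - 2^(-k/h)) / (1 - 2^(-41.5/h)). For k = 2, h = 5: 0.242 / 0.997 = 0.243.

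| Curve | k = 1 | k = 2 | k = 3 |
|---|---|---|---|
| Linear | 2% | 5% | 7% |
| Half-life 10 | 7% | 14% | 20% |
| Half-life 5 | 13% | 24% | 34% |
| Half-life 2 | 29% | 50% | 65% |
| Half-life 1 | 50% | 75% | 88% |

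The k = 1 column applies only to an afternoon start, and keeps 41.5 as an approximation. A fitted slope also excludes what is present at the first assessment, but the fraction it loses will not equal these figures exactly.

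**5. Between-arm level.** The AR-minus-control difference in mean AB across assessments contains the effect already present at the first assessment. Randomization supplies the comparison, so nothing is subtracted out. The loss in step 4 is specific to the change or slope reading.

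**The case against.** The strongest reply is that no biased analysis has been written down. The Hypothesis 1 stem calls for the randomized arms to be compared, and Hypothesis 1B is itself phrased against control. The one EMA model that is spelled out, for daily loss-of-control episodes, has a group main effect as well as a group-by-time term. A similar model for AB would keep the early effect. This stands, and it limits the point: the fault is an outcome worded as change, paired with an analysis entry that names no contrast. A reader might infer that Hypothesis 1B will be biased; the documents show only that it would be under one permitted reading.

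A reader might also infer that most of the effect is lost. That needs a half-life of about one or two trainings. The cited single-session result comes from one small study and shows that some effect can appear early, not that most of it does. Section III also expects more sessions to bring greater or more sustained reductions, which fits slower accrual and smaller losses.

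Nor does the problem extend to the main test of Aim 1. Laboratory AB has an untrained Visit 2 value, and its model adjusts for it.

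Finally, adding a phone assessment at Visit 2 and computing change from it looks like the natural remedy. As listed, however, device training follows the MEG food-cue task and the buffet test meal. The protocol gives a standard breakfast specifically to limit the influence of hunger on food AB. Change from a post-meal laboratory value to a field value would mix training with satiety and setting.

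**Conclusion.** The point holds for a secondary outcome. No untrained smartphone AB value is scheduled, whichever day the program starts, yet the outcome is defined as change over the program. If analysed as a within-program change or slope, it understates the effect by anything from about 5% to 88% with two or three prior trainings. The range is wide because the learning curve is assumed, and the documents cannot narrow it. The direction, toward no effect, assumes only that the effect accrues steadily in one direction. Two or three prior trainings assumes a full first day; one or two is possible. A between-arm comparison of level would avoid the loss but is not specified for smartphone AB. Any gain in precision from a baseline covariate cannot be sized, because the reliability the protocol quotes is for mean reaction time, not for the bias difference score.

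**What to change.** Replace the one-line smartphone entry under Hypothesis 1 with a defined test, and align the outcome wording in Section VII.c with it:

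- **Contrast:** the AR-minus-control difference in smartphone AB, averaged over the assessments, from a linear mixed model with repeated assessments within girl. If an arm-by-day term is in the model, center day so that the arm coefficient is this average difference.
- **Baseline covariate:** Visit 2 laboratory AB, already collected before training. It differs from the phone task in setting and picture pairs, so it serves as a covariate and not as the start of a change score.
- **Arm-by-day slope:** secondary, described as further change after the first trainings.
- **Exclusion:** state that the first in-program phone value is not to be used as a baseline.
- **Start:** state when the first signal is sent after Visit 2.

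This costs wording only.

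Optionally, add one 40-trial phone AB assessment at Visit 2 before any AR or control trial, used only as a covariate. It would take a few minutes; the protocol's time estimate allows about 5 minutes per prompt. As Visit 2 is listed, it would follow the test meal and the food-cue task, so it may correlate only modestly with field values.

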d. Reasons for Withdrawal/Adverse Event Reporting: Participants will be examined briefly on the phone during the initial screening, and more extensively during the screening visit (Visit #1) as well as the follow-up visits. Participants will be excluded and/or referred for treatment if appropriate, as previously described. Identification of a current and significant psychiatric disorder at the time of enrollment will result in an appropriate referral to a mental health professional and study exclusion. Noncompliance with study procedures may lead to withdrawal of study participants. Other events that may lead to study withdrawal include pregnancy or serious unanticipated complications, including development of any medical problem listed in the exclusion criteria. Please see Section 16: *Reporting of Unanticipated Problems, Adverse Events and Protocol Deviations* for more details regarding adverse event reporting.

f. Determination of Sample Size and Analytic Plan

Sample Size: Sample size estimation is based on the power analysis for the first Specific Aim. This is a pilot study to test a novel promising intervention for a targeted group of youth at high risk for adult obesity. Eighty overweight girls, 40 with LOC eating and 40 without LOC eating, will be randomized, out of 120 recruited. Meta-analytic studies of AR effect on attention bias (e.g., to appetite [food, alcohol], or threatening stimuli) in adults found large effects of AR ($d = .80 - 1.41$) on attention bias reductions (96, 97) and medium effects ($d = .51 - .61$) of AR on behavioral outcomes (96, 97). Based on recommended equations for estimating sample size (158, 159) when using general linear model, and assuming 35% attrition due to unusable visual probe or MEG data (based on pilot data and prior MEG studies in youth), this sample size will provide >80% power to detect medium to large effects (83, 152, 160).

Preliminary Analyses:

1. Anatomical MRI data processing will be done with AFNI software (see **Appendix 9**). Structural scans will be spatially normalized to standard Talairach space.
2. Raw MEG data will be filtered using third gradient reference coils with fixed weights. A broad frequency band (1-30 Hz) will be used for primary analyses, following procedures from prior MEG studies in new populations (83, 152, 160). Fixed frequency smoothing

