and transformation will be applied to obtain oscillatory power estimates. Oscillatory power activity will be calculated by subtracting the baseline activity (1000ms immediately prior to stimulus onset) from the activity evoked during the UCR and AD periods, respectively (84). The synthetic aperture magnetometry (SAM) beamformer technique (161) will be applied to produce a 3D representation of brain activity by calculating the oscillatory power activity for individual voxels (7 mm). Using the anatomical MRI, normalized SAM data will be co-registered and transformed into Talairach space in AFNI software. Based on our hypotheses, a priori brain regions will be selected for examination. Pseudo F-ratios – an index of 3D oscillatory power activity – for the regions-of-interest will be used in analyses (see **Appendix 9**).

3. EMA data will be collected using a specialized platform designed to collect EMA on mobile devices. Data are collected in a local database and transmitted to the Cloud Server in real time. Participant and study profiles are created on the Server and exported from the Server by an administrative user. On this platform, the estimated internal reliability of mean RT computed using split-half r is >.95 (156, 157).
4. *Missing Data and Attrition:* AR and control will be compared on study completion vs. early termination using logistic regression controlling for age, sex, race, lean mass, adiposity, and height (“covariates”). Multiple imputation based upon fully conditional Markov chain Monte Carlo modeling (162) will be used to impute missing data on non-EMA assessments. Primary analyses will be based upon imputed data except for EMA analyses. Sensitivity analyses will use all available data (i.e. no imputation) and maximum likelihood imputation and results will be compared across methods. Although data preprocessing and analytic methods can mitigate artifacts to some extent, excessive participant movement remains a problem. Structural MRI / MEG will be excluded if there is movement > 2.5 mm during respective sessions. At NIH, pediatric fMRI / MEG studies typically have 30-40% attrition in youth due to excessive movement. Thus, attrition rate of 35% is assumed in power analyses.

Primary Analyses:

Specific Aim 1

- a. **Hypothesis 1:** Youth randomized to AR and control conditions will be compared on:

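### The claim of over 80% power for medium to large effects reproduces only at d = 0.80; the plan's own medium effects (d = 0.51 to 0.61) have 44% to 58% unadjusted power in the 52 evaluable girls

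*Combined protocol and SAP*

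**What the plan says.** The Sample Size paragraph in section VII (Determination of Sample Size and Analytic Plan) contains these elements:

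- The basis: "Sample size estimation is based on the power analysis for the first Specific Aim", which concerns attention bias.
- The numbers: "Eighty overweight girls, 40 with LOC eating and 40 without LOC eating, will be randomized, out of 120 recruited".
- The plan's effect scale, taken from meta-analyses in adults: "large effects of AR ($d = .80 - 1.41$) on attention bias reductions" and "medium effects ($d = .51 - .61$) of AR on behavioral outcomes".
- The loss: "assuming 35% attrition due to unusable visual probe or MEG data". Item 4 of the Preliminary Analyses (Missing Data and Attrition) repeats that 35% is used in the power analyses and gives the range behind it: "pediatric fMRI / MEG studies typically have 30-40% attrition in youth due to excessive movement".
- The conclusion: "this sample size will provide >80% power to detect medium to large effects".

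The paragraph cites general power references for a general linear model. It gives no alpha, sidedness, allocation ratio, target d or baseline-outcome correlation. The Primary Analyses plan to adjust the laboratory attention-bias and MEG outcomes for their baseline values, order effects, age, race and BMI z-score. The test-meal and the 3-month BMI and adiposity models also adjust for earlier measurements.

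**The concern.** The paragraph defines medium and large by explicit ranges of d and then, in the sentence that applies the 35% loss, claims more than 80% power across both. Twenty-six girls per arm is a familiar size for d = 0.80. It is well short of what d of about 0.5 to 0.6 normally requires.

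Aim 3 makes energy intake and body composition primary outcomes, and the only effects cited for behavioural outcomes are the medium ones. An IRB member or later reader would conclude that the trial can detect medium effects, and could then take a null result as evidence against them. If the power is nearer one half, that inference is not available.

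**Working it through.** **Inputs from the plan.** 80 randomised; 35% loss (range 30% to 40%); d = 0.80 to 1.41 (large, attention bias); d = 0.51 to 0.61 (medium, behavioural outcomes).

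**Assumed because not stated.** 1:1 allocation, two-sided alpha 0.05, no gain from covariates. The last two are varied below.

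**Evaluable number.** 80 × (1 − 0.35) = 52, or n = 26 per arm.

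**Formula.** Two-sample t-test with df = 2n − 2 and noncentrality δ = d × √(n/2). Power is the probability that a noncentral t with parameter δ exceeds the critical value in absolute terms. For n = 26, √13 = 3.606, df = 50 and the critical value is 2.009.

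**The plan's figure first.** At d = 0.80, δ = 2.884 and power is 80.7%. In reverse, 80% power at d = 0.80 needs 26 per arm, and 52 / 0.65 = 80. The stated sample size is therefore what d = 0.80 alone would give under these assumptions.

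**The medium range, 26 per arm.**

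| d | δ | Power, two-sided 5% | Power, one-sided 5% | Evaluable girls for 80% (two-sided) |
|---|---|---|---|---|
| 0.51 | 1.839 | 43.8% | 56.7% | 2 × 62 = 124 |
| 0.61 | 2.199 | 57.8% | 70.0% | 2 × 44 = 88 |
| 0.80 | 2.884 | 80.7% | 88.5% | 2 × 26 = 52 |

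The smallest effect with 80% power (two-sided, unadjusted) is d = 0.79. At 35% loss, 88 and 124 evaluable correspond to 136 and 191 randomised (88 / 0.65 = 135.4; 124 / 0.65 = 190.8).

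**The plan's own loss range (two-sided).**

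| Loss | Evaluable | d = 0.51 | d = 0.61 | d = 0.80 |
|---|---|---|---|---|
| 30% | 56 | 47% | 61% | 84% |
| 40% | 48 | 41% | 54% | 77% |

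**Baseline adjustment.** With baseline-outcome correlation r, the residual SD falls by √(1 − r²), so the effective effect is d / √(1 − r²).

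- With 26 per arm, the smallest effect with 80% power becomes 0.792 × √(1 − 0.25) = 0.69 at r = 0.5 and 0.792 × √(1 − 0.49) = 0.57 at r = 0.7.
- The r needed for 80% is √(1 − (d / 0.792)²): 0.77 at d = 0.51 and 0.64 at d = 0.61.

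**Aim 3 continuous outcomes.** Loss of visual probe or MEG data need not remove a girl from the test-meal or body-composition analyses, so these were also run without that loss (two-sided).

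| Per arm | d = 0.51, unadjusted | d = 0.61, unadjusted | r needed for 80% |
|---|---|---|---|
| 40 (no loss at all) | 62% | 77% | 0.60 and 0.27 |
| 36 (assumed 10% dropout) | 57% | 72% | not computed |

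The negative binomial GEE for LOC episodes is not covered by these figures.

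**The case against.** The strongest reply is that the aim that sizes the trial is met. Aim 1 concerns attention bias, the cited effects start at d = 0.80, and power there is 81%. That stands, and neither the sample size nor the design is in question.

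Second, the plan attaches d = 0.51 to 0.61 to behavioural outcomes and the 35% loss to visual probe or MEG data, so pairing the two is a harsh reading. This is fair as far as it goes, but the plan's own sentence joins that loss to medium effects, and without any loss unadjusted power is still 62% to 77%.

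Third, the planned models adjust for baseline, so unadjusted figures understate their power. Also true. With 40 per arm, r = 0.6 gives 80% at d = 0.51 and 92% at d = 0.61. This is why the Aim 3 claim is called unverified. But no correlation is stated. The split-half reliability above 0.95 quoted for the smartphone platform is internal reliability of mean reaction time; it is not a baseline-to-follow-up correlation of the laboratory bias score.

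Other readings help only in part:

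- One-sided 5% testing leaves 57% to 70% with 52 girls. With all 80 it gives 86% at d = 0.61 but only 73% at d = 0.51.
- If medium meant Cohen's f² = 0.15, power is 78% at 52 and 81% at 56. That nearly meets the claim, but it is not the scale the paragraph uses.
- Modelling the post-program and 3-month visits jointly, assuming a constant effect and equal correlations, would lower the correlation needed: 82% at d = 0.61 with r = 0.3, and 85% at d = 0.51 with r = 0.7. The plan specifies no joint model, and it names the change to the post-program visit as the primary outcome.

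Finally, the match between 80 and d = 0.80 rests on assumed inputs, and 80 is also simply 40 plus 40 by LOC status. How the number was actually derived cannot be known from the document.

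**Conclusion.** The concern holds. From the inputs the plan states, the power claim reproduces at d = 0.80 and above but not for the range the plan itself calls medium.

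- **Attention bias and MEG (52 evaluable):** 44% to 58% at d = 0.51 to 0.61, so effects of that size would be missed about 42% to 56% of the time. The claim is rescued only by an unstated correlation of about 0.64 to 0.77.
- **Aim 3 continuous outcomes:** 62% to 77% unadjusted even with no loss. The claim may be true with r of about 0.27 to 0.60 or more, but the plan does not show it.
- **Aim 1 at d = 0.80:** supported with little margin, at 81%, falling to 77% at the 40% end of the plan's loss range.

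These figures assume 1:1 allocation, two-sided 5% and, unless noted, no covariate gain. The defect is an overstated and under-specified power statement. It should be corrected, but it does not call for a different sample size.

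**What to change.** Rewrite the power sentence so that its inputs are visible and its range matches them. For example:

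> With 80 girls randomised 1:1 and 35% unusable visual probe or MEG data (52 evaluable), a two-sided 5% test has 81% power for d = 0.80 on laboratory attention bias, assuming no gain from baseline adjustment (77% if 40% are unusable). For d = 0.51 to 0.61, unadjusted power is 44% to 58% in this set. For the Aim 3 continuous outcomes it is 62% to 77% unadjusted if all 80 contribute, and lower with ordinary dropout.

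If the sponsor's calculation relied on a baseline-outcome correlation, give its value and source for each outcome and report the adjusted power beside the unadjusted figure. If it used a different alpha, sidedness or definition of medium, state that instead and recompute.

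The cost is one paragraph of text, with no added participants, visits or analyses. The stated power for medium effects becomes less favourable, and null results on those outcomes would have to be read accordingly.
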